9.2.1. Inclusion and Exclusion Criteria

Cohort 1

Inclusion Criteria

1. Male and female subjects between 18 and 65 years of age, inclusive
2. Subject must provide signed informed consent prior to any study-related procedures
3. Subjects of childbearing potential must agree to use medically accepted methods of contraception during the study and for 90 days after last co-administration of ATB200 and AT2221
4. Subject has a diagnosis of Pompe disease based on documented deficiency of GAA enzyme activity or by *GAA* genotyping
5. Subject has received ERT with alglucosidase alfa (Myozyme/Lumizyme) for the previous 2 to 6 years, inclusive
6. Subject is currently receiving alglucosidase alfa (Myozyme/Lumizyme) at a frequency of once every other week
7. Subject has received and completed the last 2 infusions without a drug-related adverse event resulting in dose interruption
8. Subject must be able to walk between 200 and 500 meters on the 6MWT
9. Upright FVC must be 30% to 80% of predicted normal value

Exclusion Criteria

1. Subject has received any investigational therapy including adjunctive therapy for Pompe disease, other than alglucosidase alfa within 30 days or 5 half-lives of the therapy or treatment, whichever is longer, prior to the Baseline Visit, or anticipates doing so during the study
2. Subject has received treatment with prohibited medications (see Section 8.7) within 30 days of the Baseline Visit
3. Subject, if female, is pregnant or breastfeeding at screening
4. Subject, whether male or female, is planning to conceive a child during the study
5. Subject requires invasive ventilatory support
6. Subject uses noninvasive ventilatory support \geq 6 hours a day while awake
7. Subject has a medical or any other extenuating condition or circumstance that may, in the opinion of the investigator or the Medical Monitor, pose an undue safety risk to the subject or compromise his/her ability to comply with protocol requirements
8. Subject has a history of anaphylaxis to alglucosidase alfa
9. Subject has a history of high sustained anti-rhGAA antibodies (see Section 10.4)
10. Subject has a history of allergy or sensitivity to miglustat or other iminosugars
11. Subjects with active systemic autoimmune disease such as lupus, scleroderma, or rheumatoid arthritis; all subjects with autoimmune disease must be discussed with the Amicus Medical Monitor

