12.1.3. Exploratory Endpoints

- Anti-rhGAA antibodies (total and neutralizing)
- Cross-reactivity of anti-rhGAA antibodies to alglucosidase alfa
- Pro-inflammatory cytokines and other biomarkers of immune system activation
- PD biomarkers: urinary Hex4 and serum CK
- Evaluation of anti-rhGAA antibody impact on AUC and CL_T after at least 18 months of ATB200/AT2221 treatment as compared to AUC and CL_T after the first and third doses of 20 mg/kg ATB200 + 260 mg AT2221

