12.4.4. Statistical Methods

12.4.4.1. Statistical Plan for PK Data

For the purpose of summarizing drug concentration/activity data, all BLQs will be set to zero (0) values. Drug concentration/activity data will be summarized with descriptive statistics including arithmetic means, standard deviations (SDs), coefficients of variation, median, minimum, and maximum, standard error of the mean, and 5th and 95th percentiles. Pharmacokinetic parameters will be summarized with descriptive statistics including N (number of subjects in the treatment population), arithmetic means, SDs, coefficients of variation, median, minimum, and maximum. Geometric means will be calculated for AUC_{0-t}, AUC_{0-∞}, and C_{max}.

The following statistical analysis of variance (ANOVA) comparisons will be performed to assess the relative bioavailability on PK parameters C_{max}, AUC_{t-0}, and AUC_{0-∞} for plasma GAA activity levels and total GAA protein concentrations:

Cohort 1 Subjects:

- 20 mg/kg ATB200 + 130 mg AT2221 (single dose) versus 20 mg/kg ATB200 alone
- 20 mg/kg ATB200 + 260 mg AT2221 (single dose) versus 20 mg/kg ATB200 alone
- 20 mg/kg ATB200 + 130 mg AT2221 (single dose) versus 20 mg/kg ATB200 + 260 mg AT2221 (single dose)
- 20 mg/kg ATB200 + 130 mg AT2221 (multiple dose) versus 20 mg/kg ATB200 + 260 mg AT2221 (multiple dose)
- 20 mg/kg ATB200 + 130 mg AT2221 (single dose) versus 20 mg/kg ATB200 + 130 mg AT2221 (multiple dose)
- 20 mg/kg ATB200 + 260 mg AT2221 (single dose) versus 20 mg/kg ATB200 + 260 mg AT2221 (multiple dose)

Cohort 3 Subjects:

- 20 mg/kg ATB200 + 260 mg AT2221 (single dose) versus 20 mg/kg ATB200 + 260 mg AT2221 (multiple dose)

Cohort 3 versus Cohort 1 Subjects:

- 20 mg/kg ATB200 + 260 mg AT2221 (multiple dose) versus 20 mg/kg ATB200 + 260 mg AT2221 (multiple dose)
- 20 mg/kg ATB200 + 260 mg AT2221 (single dose) versus 20 mg/kg ATB200 + 260 mg AT2221 (single dose)
- 20 mg/kg ATB200 + 260 mg AT2221 (multiple dose) versus 20 mg/kg ATB200 alone
- 20 mg/kg ATB200 + 260 mg AT2221 (single dose) versus 20 mg/kg ATB200 alone

Following ln-transformation, plasma GAA activity levels and total GAA protein concentration C_{max}, AUC_{0-∞}, and AUC_{0-t}, will be separately analyzed using a fixed effects model with fixed effect terms for treatment or subject group. Point estimates, and their associated 90% confidence

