intervals (CIs) will be constructed for the differences, test treatment or subject group, and reference treatment or subject group. The point estimates and their associated 90% CIs will then be back-transformed to provide point estimates and 2-sided 90% CIs for the ratios of test/reference, on the original scale.

A dose proportionality assessment will be performed using the power method for 5, 10, and 20 mg/kg ATB200 in Stage 1 and for 130 and 260 mg AT2221 in Stage 2.

For the dose proportionality analysis, in Stage 1, the reference treatment will be 5 mg/kg ATB200, and the test treatments will be 10 mg/kg and 20 mg/kg ATB200 and, in Stage 2, the reference treatment will be 130 mg AT2221, and the test treatment will be 260 mg AT2221. For the ANOVA comparisons within Stage 2, the reference treatments will be single-dose, and the test treatments will be multiple-dose, and between Stages 1 and 2, the reference treatment will be 20 mg/kg ATB200 alone, and the test treatments will be 20 mg/kg ATB200 + 130 mg AT2221 and 20 mg/kg ATB200 + 260 mg AT2221. For between subject comparisons, the reference group will be Cohort 1 subjects, and test group will be Cohort 3 subjects.

For effect of anti-rhGAA antibody on total GAA protein exposures and plasma clearance, statistical comparisons between after at least 18 months of treatment in Stage 3 versus the first and third doses of treatment with 20 mg/kg ATB200 + 260 mg AT2221 will be performed on estimated plasma total GAA protein AUCs, plasma clearance, and 4-, 6-, 8-, and 12-hour plasma total GAA protein concentrations. PK data from both cohorts will be pooled for the statistical comparisons.

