12.4.4.4. Immunological Analyses

The effect of immunogenicity results on PK, PD, efficacy, and safety will be explored. Further details will be provided in the SAP. Assessments may include the following:

- Baseline anti-rhGAA antibody-positive (total and neutralizing) subjects as a percentage of the total number of subjects whose baseline samples were tested for anti-rhGAA antibodies
- Antibody range (median and interquartile range [IQR]) of the baseline anti-rhGAA antibody-positive samples (total and neutralizing)
- Percentage of baseline anti-drug antibody-positive subjects with significant increases in anti-rhGAA antibodies (total and neutralizing) after biologic drug administration (ie, when any one sample taken after the initial drug administration has an anti-rhGAA titer that is greater than the baseline titer by a scientifically reasonable margin)
- anti-rhGAA antibody-positive subjects at every visit as a percentage of the total number of subjects whose baseline samples were tested for anti-rhGAA (total and neutralizing)
- anti-rhGAA antibody-positive subjects at every visit as a percentage of the total number of subjects whose samples were tested at that visit for anti-rhGAA (total and neutralizing)
- Antibody range (median and IQR) of the anti-rhGAA antibody-positive samples at every visit (total and neutralizing)
- Kinetics and duration of anti-rhGAA antibodies over time in the study (total and neutralizing)
- Evaluation of high, mid, low, or no antibody groups (total and neutralizing) on plasma GAA activity levels and total GAA protein concentration C_{max} AUC, and CL over time in the study
- Evaluation of high, mid, low, or no antibody (total and neutralizing) groups on PD assessments (Hex4 and CK) over time in the study
- Cytokine levels and changes over time in the study

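### The contrast that the protocol labels as the antibody effect on GAA exposure contains no antibody measure, so it estimates change over time, pooled over two cohorts with different starting points

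*Protocol*

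**What the plan says.** Protocol 12.4.4.1 introduces the analysis with "For effect of anti-rhGAA antibody on total GAA protein exposures and plasma clearance, statistical comparisons between after at least 18 months of treatment" and goes on "in Stage 3 versus the first and third doses of treatment with 20 mg/kg ATB200 + 260 mg AT2221 will be performed". The quantities compared are estimated AUC, plasma clearance, and total GAA protein concentrations at 4, 6, 8 and 12 hours. It then says "PK data from both cohorts will be pooled for the statistical comparisons"; the cohorts are 1 and 3, the only ones with PK sampling. The exploratory endpoint in 12.1.3, "Evaluation of anti-rhGAA antibody impact on AUC" and clearance, is defined by the same late-versus-early comparison. The synopsis, under Criteria for Evaluation, describes the comparison neutrally, as late exposure against exposure at the first and third doses, with no mention of antibodies.

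Other places in the documents bear on the point:

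- Protocol 12.4.4.4 commits to exploring the effect of immunogenicity on PK. It lists "Evaluation of high, mid, low, or no antibody groups (total and neutralizing) on plasma GAA activity levels", together with total protein exposure and clearance over time, among assessments that are optional. The synopsis says for Cohort 1 that the effect of immunogenicity results on PK will be evaluated.
- SAP 3.3 keeps the impact of antibodies on GAA total protein exposure as an exploratory objective for Stages 3 and 4.
- SAP 8.1 refers to Protocol 12.4.4.1 for the noncompartmental PK work and plans to copy the PK summaries from the first interim report into the final report. SAP 8.2 assigns the impact of antibodies on PK to a separate Modeling and Simulation Plan, which is not among the documents.

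**The concern.** The question is whether anti-rhGAA antibodies change exposure and clearance. The comparison given as the answer would be computed identically if no antibody sample had ever been drawn.

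A ratio near 1 could be reported as showing that antibodies do not affect exposure, when an effect was present at both times and cancelled. A ratio away from 1 could be reported as an antibody effect, when something else changed over 18 months or more. Because PK summaries are to be carried into the final report from an interim report, a label attached to this contrast could be carried over with them.

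**Working it through.** The plan states no sample size, power or error rate for this comparison, so there is no figure to reproduce. The check is what the contrast estimates.

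**Inputs from the documents**

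- Planned numbers: 11 in Cohort 1 and 5 in Cohort 3 (Protocol Table 8), so at most 16.
- Cohort 1 entry: "Subject has received ERT with alglucosidase alfa (Myozyme/Lumizyme) for the previous 2 to 6 years, inclusive". Only a history of high sustained titre is excluded (9.2.1, 10.4), so lower titres are allowed at entry.
- Cohort 1 reference doses: Visits 9 and 11, the first and third with 260 mg AT2221. Table 9 shows ATB200 infusions at Visits 3 to 8, which is 3 in Stage 1 + 3 in Period 4 = 6 before the first reference dose.
- Cohort 3 reference doses: Day 1 and Week 4. Day 1 is the first ERT exposure of any kind.
- PK method: 12.4.3.2 gives noncompartmental analysis for serial samples; 10.1.8 gives compartmental or population modelling for the sparse samples at 18 months or later.
- The only model described in 12.4.4.1 is for the ANOVA comparisons, "using a fixed effects model with fixed effect terms for treatment or subject group". It has no antibody term, and it is not expressly applied to the late contrast.

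**What the contrast estimates**

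For a subject in cohort *c*, write the late-minus-reference difference in ln AUC as

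D = t_c + m + β·ΔA + error,

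where t_c is non-antibody change over time, m is any shift from a change of estimation method, β is the antibody effect on the ln scale, and ΔA is the change in antibody status. Let ΔP_c be the mean of ΔA in cohort *c*. With weights 11/16 = 0.6875 and 5/16 = 0.3125, the pooled mean is

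E(D) = 0.6875·t_1 + 0.3125·t_3 + m + β·(0.6875·ΔP_1 + 0.3125·ΔP_3).

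One estimate carries drift, method shift and antibody effect, and nothing in the contrast separates them.

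**Illustrations** (all effect sizes and conversion shares are assumptions; m = 0 throughout)

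1. No antibody effect, exposure down 10% or 20% from another cause: pooled ratio 0.90 or 0.80, labelled as the antibody effect.
2. Antibody ratio 0.70, no drift, all of Cohort 3 newly positive (ΔP_3 = 1):
   - no Cohort 1 subject changes status, ΔP_1 = 0: 0.70^0.3125 = 0.895;
   - half of Cohort 1 newly positive, ΔP_1 = 0.5: 0.70^(0.34375 + 0.3125) = 0.70^0.65625 = 0.791;
   - all of Cohort 1 newly positive, ΔP_1 = 1: 0.70.
3. Antibody ratio 0.75 with half the subjects newly positive gives 0.75^0.5 = 0.866. An upward drift of 1/0.866 = 1.155 brings the pooled ratio to 1.00, and the effect disappears.

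The range in item 2 turns on ΔP_1, which the documents do not give.

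**Measured concentrations**

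The sparse schedule (Table 15) samples at 1, 5, 6, 7, 9 and 13 hours after AT2221, to be shifted one hour earlier. That gives 0, 4, 5, 6, 8 and 12 hours after infusion start. The 4-, 6-, 8- and 12-hour comparisons therefore use measured values at hours that are also in the serial schedule (Table 14). For them m = 0 whatever method is used for AUC. The drift and cancellation problems remain.

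**The case against.** The strongest reply is that the governing analysis may lie elsewhere. SAP Section 2 says the SAP supersedes the protocol's methods, and SAP 8.2 moves antibody impact on PK to a Modeling and Simulation Plan. That plan may use titre as an input. This stands: nothing here shows that the sponsor's operative analysis lacks an antibody measure. A reader might infer that the plan contains no antibody-based exposure analysis at all. The documents do not support that, since 12.4.4.4 lists one as an option and the synopsis commits to evaluating the question in Cohort 1. What does not fall away is that 12.1.3 and 12.4.4.1 attach the antibody label to a contrast that cannot bear it.

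Second, prior ERT does not establish that Cohort 1 was antibody-positive, and because high sustained titres are excluded, titres could still rise on treatment. This stands too. Cancellation in Cohort 1 is possible but not shown, and the inference that most of the sample could not reveal an effect goes too far.

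Third, no text says outright that the early AUC in this contrast is the noncompartmental one. Both times could be estimated from one model. The change of method is a risk for AUC and clearance only if both methods are used.

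Fourth, 12.2 specifies no formal hypotheses, and the "2-sided 90% CIs for the ratios of test/reference, on the original scale" are stated for the ANOVA ratios, not expressly for this contrast. It would be tempting to quote a false-rejection rate or a loss of power. Any such figure would depend on assumed variances, antibody shares and drift. A comparison by antibody status could itself mislead if conversion coincided with cohort, because a drift confined to Cohort 3 would then look like an antibody effect.

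**Conclusion.** The point holds as one of labelling and estimand. As written, the pooled late-versus-early contrast estimates change in exposure over time. It equals an antibody effect only if nothing else changes, no method shift enters, and antibody status goes from negative to positive in every subject. Pooling adds a further difficulty: Cohort 3 is compared with its first ERT exposure, and Cohort 1 with a point after years of ERT and six ATB200 infusions.

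The direction follows from the wording and needs no numerical assumption. The size is not determinable from the documents; the ratios above are illustrations under stated assumptions.

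The consequence is limited: the endpoint is exploratory, no hypothesis is tested, and a proper antibody analysis may exist in the separate plan. This is a change worth considering, not a flaw that undermines the study.

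**What to change.** - **Relabel and split.** In Protocol 12.1.3 and 12.4.4.1, and in any text on this contrast copied from the first interim report into the final report, call the ratio change in exposure over time and show it for Cohort 1 and Cohort 3 separately.
- **Make antibody the input.** Base any antibody statement on titre or neutralizing status at the PK visits. Either make the titre-group analysis in 12.4.4.4 definite, or relate within-subject change in ln AUC and ln clearance to change in log titre. Use within-cohort variation, because conversion may coincide with cohort. Antibody samples are scheduled at the reference visits and at Stage 3 and 4 assessment visits (Tables 9, 10 and 12). If the sparse sample was taken at a visit without a titre, use the nearest one and say so.
- **Use one method.** Estimate early and late AUC and clearance the same way, and keep the measured 4-, 6-, 8- and 12-hour concentrations alongside.
- **Check the separate plan first.** If the Modeling and Simulation Plan already does the second and third items, only the relabelling remains.

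The cost is wording plus, at most, one re-analysis of data already scheduled for collection. The downside is precision: with at most about 16 subjects, and possibly fewer (Protocol Table 6 has 9 Cohort 1 subjects with a Month 18 walk test), the intervals will be wide. Results should be reported as estimates only.

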12.4.4.2. Efficacy Analyses

Details of the analysis methodology for all non-PK endpoints will be provided in the main SAP for the study.

In general, descriptive statistics will be provided for all efficacy endpoints. Continuous variables will be summarized using the number of observations (n), mean, standard deviation, median, minimum, and maximum, while categorical variables will be summarized using frequency and percentages. The absolute and percent changes from baseline for the continuous efficacy variables will be similarly summarized.

Each cohort will have its own baseline, and analysis will be performed by cohort and overall. In addition, summary analyses will be performed by combining Cohort 1, 3, and 4 for ambulatory subjects, or by combining Cohort 1 and 4 for ERT-experienced subjects. For Cohort 1, the analysis will also be provided by treatment dosing regimen. The visit values and the change from baseline to the post-baseline assessment will be analyzed by scheduled visit. The 95% CI (for the mean change from baseline and/or median difference) by scheduled visit will be provided for summary purposes only.

12.4.4.3. Safety Analyses

Adverse events and concomitant medications terms will be coded using Medical Dictionary for Regulatory Activities (MedDRA) version 16.1 or higher and WHO Drug Dictionary.

In general, TEAEs will be grouped by MedDRA System Organ Classes and by Preferred Terms. Summary statistics will be provided by cohort for AEs, ECG shift changes, vital signs shift changes, and clinical laboratory shift data based on the potentially CS values defined in

Appendix 2. In addition, summary statistics (n, mean, median, SD, minimum, and maximum) will be provided for values at each visit and changes from baseline at each visit for ECG, vital signs, and clinical laboratory assessments by cohort.

Prior and concomitant medications will also be summarized by cohort. A by-subject listing of protocol deviations will be provided.

12.4.4.4. Immunological Analyses

The effect of immunogenicity results on PK, PD, efficacy, and safety will be explored. Further details will be provided in the SAP. Assessments may include the following:

- Baseline anti-rhGAA antibody-positive (total and neutralizing) subjects as a percentage of the total number of subjects whose baseline samples were tested for anti-rhGAA antibodies
- Antibody range (median and interquartile range [IQR]) of the baseline anti-rhGAA antibody-positive samples (total and neutralizing)
- Percentage of baseline anti-drug antibody-positive subjects with significant increases in anti-rhGAA antibodies (total and neutralizing) after biologic drug administration (ie, when any one sample taken after the initial drug administration has an anti-rhGAA titer that is greater than the baseline titer by a scientifically reasonable margin)
- anti-rhGAA antibody-positive subjects at every visit as a percentage of the total number of subjects whose baseline samples were tested for anti-rhGAA (total and neutralizing)
- anti-rhGAA antibody-positive subjects at every visit as a percentage of the total number of subjects whose samples were tested at that visit for anti-rhGAA (total and neutralizing)
- Antibody range (median and IQR) of the anti-rhGAA antibody-positive samples at every visit (total and neutralizing)
- Kinetics and duration of anti-rhGAA antibodies over time in the study (total and neutralizing)
- Evaluation of high, mid, low, or no antibody groups (total and neutralizing) on plasma GAA activity levels and total GAA protein concentration C_{max} AUC, and CL over time in the study
- Evaluation of high, mid, low, or no antibody (total and neutralizing) groups on PD assessments (Hex4 and CK) over time in the study
- Cytokine levels and changes over time in the study

12.4.4.5. Baseline Demographic and Subject Characteristics

Baseline demographics and subject characteristics will be presented for all subjects included in the statistical analysis. Analyses will also be performed separately for subjects in Cohorts 1, 2, 3, and 4.

Functional assessments at baseline will be summarized for all subjects and will include the following:

- For subjects in Cohorts 1, 3, and 4: Motor function tests (Gower's Maneuver, 6MWT, 10MWT, GSGC, TUG, 4-stair climb), muscle strength tests (MRC and hand-held dynamometer [for both upper and lower limbs]), and PFTs (FVC, MIP, MEP, and SNIP)
- For subjects in Cohort 2: muscle strength tests (MRC and hand-held dynamometer [upper limbs only]) and PFTs (FVC, MIP, MEP, and SNIP [in subjects with noninvasive ventilatory support only])
- For all cohorts: PROs (FSS, RHS, and R-PAct Scale)

12.4.4.6. Subject Disposition

A summary table will be provided for subjects enrolled, included in all statistical analyses, completed each visit, discontinued the study, and reasons for discontinuation.

13. STUDY TREATMENTS

13.1. Description of Study Treatments

ATB200 (recombinant human acid α -glucosidase [rhGAA]) functions as ERT.

AT2221 (*N*-butyldeoxynojirimycin) is an iminosugar that functions as a selective pharmacological chaperone of GAA or rhGAA.

Table 20: Investigational Product

Investigational Product		
Product Name	ATB200	AT2221
Dosage Form	lyophilized powder for intravenous infusion	hard gelatin capsule
Unit Dose	15 mg/mL	65 mg
Route of Administration	intravenous infusion	oral
Physical Description	sterile, nonpyrogenic, white to off-white lyophilized cake or powder supplied in single-use, clear 20 mL (cc) glass vials	White, size 2, hard gelatin capsules supplied in 40 cc HDPE bottles
Manufacturer	WuXi AppTec Biopharmaceuticals Co., Ltd [name]	AAI Pharma [name]

